19.3 Informed Consent

The ICH issued guidelines to provide protection for human subjects in clinical investigations. The ICH Tripartite Guideline for Good Clinical Practice establishes the general requirements for informed consent. Each subject will be provided with oral and written information in a language they can understand that describes the nature and duration of the study. Before undergoing screening, each subject must consent in writing to study participation. The patient will sign and personally date the subject ICF. The person rendering consent will also sign and personally date the subject ICF as the person who obtained the consent of the subject. In the case of a minor, according to the local definition (e.g., below 16 or 18 years of age), a parent or legal representative should also sign and date the ICF. Local regulations should be followed for consenting subjects under the age of consent and original signed assent, when applicable, will be retained with the study center's records with the subject's ICF. The original signed subject ICF will be retained with the study center's records. Each subject will receive a copy of her signed subject ICF. In addition, the PI, or his or her designee, must document in the case history that informed consent was obtained before study participation.

19.4 Future Use of Samples

Biological samples collected during the study, including *Candida* spp. isolates (see [Section 14.8](#) and [Section 14.10](#)), may be maintained in repositories for potential future use. Future research of *Candida* isolates may include *in vitro* susceptibility testing of new or existing antifungals or analysis of mechanisms of resistance. All samples will be identified only by a coded number to maintain subject confidentiality.

19.5 Subject Privacy and Subject Confidentiality

All laboratory specimens, evaluation forms, reports, and other records that leave the site will be identified only by a coded number to maintain subject privacy and confidentiality. All records will be kept in a locked file cabinet. All computer entry and networking programs will be performed with coded numbers only. Clinical information will not be released without written permission of the subject, except as necessary for monitoring by the medical monitor, IRB/EC, the Food and Drug Administration (FDA), the Sponsor or where required by law. All local privacy laws must be followed.

19.6 Study Termination

The PI, the sponsor, the FDA, and the IRB/EC each reserve the right to terminate the study in the interest of subjects' safety and welfare. The sponsor reserves the right to terminate the study at any time for administrative reasons.

19.7 Financial Disclosure

The financial interests of all investigators from all participating clinical centers must be collected prior to study initiation and 1 year following the completion of the clinical trial.

21.0 Appendices

Appendix A: Prohibited Medications and Medications to be Administered with Caution

Prohibited Medications

The use of any topical vaginal corticoids and topical vaginal contraceptives is prohibited during the study. No systemic or topical vaginal antifungal treatment other than the study drug is allowed during the study unless used as rescue medication after the subject has been documented as not responding to study drug. No investigational drugs other than the study drug are allowed within 30 days before Screening and for the entire duration of the study. In addition, the medications listed below are also prohibited.

Strong CYP3A4/5 inhibitors and CYP3A4/5 inducers

CYP	Strong Inhibitors ^a	Inducers ^a	
3A4/5	
 • boceprevir • clarithromycin • conivaptan • indinavir • lopinavir • mibefradil 	
 • nefazodone • nelfinavir • ritonavir • saquinavir • telaprevir • telithromycin 	
 • avasimibe • carbamazepine • phenytoin • rifampin • St. John's wort • long-lasting barbiturates

- a. The CYP3A4/5 inhibitors and CYP3A4/5 inducers listed in this table are not permitted during the 7 days prior to enrollment and during study treatment until TOC.

P-glycoprotein (P-gp) substrates

P-gp Drug Substrates ^a
digoxin, colchicine

- a. The P-gp substrates listed in this table are not permitted during the 48 hours prior to enrollment or during study treatment

Medications to be administered with Caution and Monitored as Appropriate

CYP3A4 substrates

CYP	Substrates
3A4	
In vitro, ibrexafungerp (SCY-078) was an inhibitor of CYP3A mediated metabolism of midazolam, but was only a weak inhibitor of metabolism of testosterone. The clinical significance of this inhibition is unknown; caution should be exercised when administering ibrexafungerp (SCY-078) with drugs known to be CYP3A sensitive substrates with narrow therapeutic index, such as midazolam and cyclosporine.
 
Subjects receiving sirolimus, tacrolimus, warfarin, cyclosporine or amiodarone are permitted for enrollment in the study and these medications may be administered concomitantly with ibrexafungerp (SCY-078) with close monitoring. Dosing adjustments and subsequent monitoring of sirolimus and warfarin should be undertaken in accordance with product prescribing information for the respective agents.

OATP1B3 substrates

OATP	Substrate
1B3	
In vitro, ibrexafungerp (SCY-078) is an inhibitor of the OATP1B3 liver uptake transporter. The clinical significance of this inhibition is unknown; however, there is a potential risk for increased exposure of the concomitant medications (arising from lowered hepatic clearance) when administering ibrexafungerp (SCY-078) with drugs known to be OATP1B3 selective substrates. Therefore, caution should be exercised when administering ibrexafungerp (SCY-078) with drugs known to be OATP1B3 selective substrates such as telmisartan, including monitoring the subject for signs of overexposure associated with the concomitant medications as described in the product prescribing information.

Sources:

- FDA Draft Guidance for Industry. Drug Interaction Studies – Study Design, Data Analysis, and Implications for Dosing and Labeling. 2012.
- Drug interactions in infectious disease by Stephen C. Piscitelli, Keith Rodvold (2007)
- UCSF-FDA Transportal

Appendix B: Vulvovaginal Signs and Symptoms Scale

SIGNS:

To be rated by the investigator during the vulvovaginal examination

Sign	Absent 0	Mild 1	Moderate 2	Severe 3
Edema				
Erythema				
Excoriation or fissures				

Definitions:

Absent: none

Mild: slight

Moderate: definitely noticeable

Severe: marked, intense

SYMPTOMS:

To be rated by the subject

Symptom	Absent 0	Mild 1	Moderate 2	Severe 3
Burning				
Itching				
Irritation				

Definitions:

Absent: I have no discomfort (i.e., burning, itching, irritation)

Mild: I have some discomfort (i.e., burning, itching, irritation), but it does not bother me much

Moderate: I have discomfort (i.e., burning, itching, irritation), which is annoying, but not enough to affect what I am doing

Severe: I have discomfort (i.e., burning, itching, irritation), which is annoying enough to affect what I am doing

AVVC	acute vulvovaginal candidiasis
BID	twice daily
BMI	body mass index
CFR	code of Federal Regulations
CMH	Cochran Mantel Haenszel
CRF	case report form
eCRF	electronic case report form
eDISH	evaluation of drug induced serious hepatotoxicity
FU	follow-up
ICF	Informed Consent Form
ID	identification
IRB	Institutional Review Board
ITT	intent-to-treat
IWRS	Interactive web-based response system
IVRS	interactive voice response system
KOH	potassium hydroxide
mBOCF	modified baseline observation carried forward
MedDRA	Medical Dictionary for Regulatory Activities
MIC	minimum inhibitory concentration
MIC50	minimum inhibitory concentration required to inhibit the growth of 50% of organisms
MIC90	minimum inhibitory concentration required to inhibit the growth of 90% of organisms
mITT	modified intent to treat
NRI	non-responder imputation
PI	principal investigator
PP	per protocol
PT	preferred term
SAE	serious adverse event
SAP	Statistical Analysis Plan
SD	standard deviation
SOC	system organ class
SS	safety set
TOC	test of cure
UK	unknown
UNK	unknown
VSS Scale	vulvovaginal signs and symptoms scale
VVC	vulvovaginal candidiasis

1. Introduction

Vulvovaginal candidiasis (VVC) is a common fungal infection caused by *Candida spp.* and is a significant morbidity condition in women from all social classes. VVC can be an acute, chronic, recurrent, or persistent condition that can involve the vulva, vagina, and adjacent crural areas. It affects about 75% of women on at least one occasion over a lifetime.

Current treatments for VVC include topical antifungals and the use of prescription oral antifungals such as a single dose of fluconazole. According to previous clinical studies, a single dose of fluconazole is able to provide an acceptable therapeutic outcome for more than half of the treated individuals, but the emergence of fluconazole resistance among *C. albicans* isolates and the frequency of cases caused by *C. glabrata*, a strain naturally less susceptible to fluconazole, signals the need for new therapeutic approaches.

Additionally, recurrence of VVC after fluconazole therapy is not uncommon and these exacerbations often involve the same microorganism identified in the initial episode, suggesting that a small number of *C. albicans* remain as a reservoir in the vagina after completion of azole therapy, becoming the source of subsequent exacerbations.

New curative approaches are needed, particularly involving agents with fungicidal activity (i.e., that are able to kill the fungus) and activity against fluconazole-resistant strains, so that the causative yeasts can be eradicated. A new therapeutic approach with these characteristics would be expected to result in improved short-term and potentially long-term outcomes for this condition.

Ibrexafungerp (formerly known as SCY-078) is a member of a new class of antifungal agents and is an orally active, semi-synthetic, triterpenoid derivative of the natural product enfumafungin. Time-kill studies have demonstrated that ibrexafungerp (SCY-078) has in vitro fungicidal activity against *Candida spp.* isolates similar to that observed with the echinocandins. In addition, the safety and efficacy of ibrexafungerp (SCY-078) have been proved through many non-clinical programs and phase I/II studies.

This study aims to provide evidence of the efficacy and evaluate the safety of oral SCY-078 as a new class of antifungal agent with fungicidal activity against *Candida spp.* in the treatment of subjects with acute vulvovaginal candidiasis (AVVC).

2. Objectives

2.1. Primary Objectives

To evaluate the efficacy of oral ibrexafungerp versus placebo in subjects with AVVC by comparing the clinical outcomes of ibrexafungerp and placebo.

2.2. Secondary Objectives

- To evaluate the efficacy of oral ibrexafungerp versus placebo in subjects with AVVC based on mycological and clinical outcomes
- To evaluate the safety and tolerability of oral ibrexafungerp versus placebo in subjects with AVVC

3. Investigational Plan

3.1. Overall Study Design and Plan

This is a Phase 3, randomized, multicenter, double-blind, placebo-controlled study to evaluate the efficacy and safety of oral ibrexafungerp compared to placebo in female subjects 12 years and older with AVVC.

Approximately 366 eligible subjects will be enrolled and randomized in a 2:1 ratio to either ibrexafungerp (300-mg dose twice a day [BID]) or matching placebo administered BID for 1 day. The primary objective of this study is to evaluate the efficacy of oral ibrexafungerp in subjects with AVVC by comparing the clinical outcomes of ibrexafungerp and placebo.

The study will consist of a Screening visit, a Baseline visit on Day 1 (these visits may occur on the same day), a TOC visit on Day 11 (± 3) and a FU visit on Day 25 (± 4).

The schedule of study assessments is presented in [Appendix 1](#).

3.2. Study Endpoints

3.2.1. Primary Endpoints

Efficacy as measured by the percentage of subjects with clinical cure (complete resolution of signs and symptoms) at the test-of-cure (TOC) visit.

3.2.2. Secondary Efficacy Endpoints

Efficacy as measured by:

- The percentage of subjects with mycological eradication (negative culture for growth of *Candida* species) at the TOC visit;
- The percentage of subjects with clinical cure and mycological eradication (responder outcome) at the TOC visit;

- The percentage of subjects with complete resolution of symptoms at the Follow-up (FU) visit;
- The percentage of subjects with clinical improvement (partial or complete resolution of signs and symptoms with total composite score no greater than 1) at the TOC visit;
- The absolute change in signs and symptoms score from Baseline to TOC and FU visits.

Safety and tolerability as measured by:

- Adverse events (AEs);
- Vital signs;
- Physical examination;
- Treatment discontinuation;
- Safety laboratory tests.

3.3. Treatments

At Baseline (Day 1), eligible subjects will be randomized in a 2:1 ratio to one of the following two treatment groups:

- Oral ibrexafungerp 300-mg dose BID for 1 day
- Oral ibrexafungerp matching placebo BID for 1 day

For the purpose of maintaining treatment blinding, all subjects randomized to the placebo group will receive matching ibrexafungerp placebo tablets. Subjects will receive their first dose of study drug at the site. The second study drug dose will be self-administered by the subjects approximately 12 hours later at home on Baseline (Day 1). If administering the first dose at the study center would complicate the administration of the second dose 12 hours later (e.g. first dose at 3 p.m. will require second dose at 3 a.m.), the subject can self-administer both doses at home to allow for a more convenient dosing schedule (e.g., 8 p.m. and 8 a.m.). Subjects will record study drug dosing details in their study diary.

4. General Statistical Considerations

Continuous data will be described using descriptive statistics (i.e. n, mean, standard deviation (SD), median, minimum, and maximum). Categorical data will be described using the subject count and percentage in each category. For the summary statistics of all numerical variables unless otherwise specified, minimum and maximum will be displayed to the same level of precision as reported. Mean and median will be displayed to one level of precision greater than the data collected. Standard deviation / standard error will be displayed to two levels of precision greater than the data collected. P-values will be rounded to three decimal places. If a p-value is less than 0.001 it will be reported as “<0.001.” If a p-value is greater than 0.999 it will be reported as “>0.999.” Data will be displayed in all listings sorted by treatment group.

Subjects will be identified in the listings by the subject identification number concatenated with the investigator number.

When count data are presented, the percentage will be suppressed when the count is zero in order to draw attention to the non-zero counts. A row denoted “Missing” will be included in count tabulations where specified on the shells to account for dropouts and missing values. The denominator for all percentages will be the number of subjects in that treatment within the analysis set of interest, unless otherwise specified.

Unless otherwise specified, baseline will be defined as the last non-missing assessment prior to or on the date (and time if appropriate) of the first dose of study drug. Change from baseline is defined as: post-baseline value – baseline value.

The study day will be calculated as follows:

If the assessment date occurs on or after the date of the first dose of study drug:

$$\text{Study day} = \text{assessment date} - \text{first dose date} + 1.$$

If the date of interest occurs before the date of the first dose of study drug:

$$\text{Study day} = \text{assessment date} - \text{first dose date}$$

There is no study day 0.

All analyses will be conducted using SAS Version 9.3 or higher. All statistical tests will be two-sided and interpreted at a 5% significance level.

4.1. Sample Size

The primary endpoint of the study is the percentage of subjects achieving a clinical cure at the TOC visit. Assuming clinical cure rates of 50% and 30% for ibrexafungerp and placebo administered in a 2:1 ratio, respectively, approximately 282 subjects will provide 90% power to detect a difference between ibrexafungerp and placebo based on a Pearson’s Chi-squared test with a Type 1 error rate of 5%. Because it is expected that approximately 20% of subjects may not have a mycological culture-confirmed infection at Baseline and approximately 10% may withdraw early

from the study, an additional 84 subjects are added for a total of 366 subjects (244 subjects randomized to ibrexafungerp and 122 subjects, to placebo).

4.2. Randomization, Stratification and Blinding

Approximately 366 eligible subjects will be enrolled and randomized in a 2:1 ratio to one of the following two study treatment groups:

- Oral ibrexafungerp 300-mg dose BID for 1 day
- Oral ibrexafungerp matching placebo BID for 1 day

An interactive response system (voice or web-based) will be used to administer the randomization schedule. Biostatistics will generate the randomization schedule using SAS® software Version 9.3 or later (SAS Institute Inc, Cary, North Carolina) for IWRS/IVRS, which will link sequential subject randomization numbers to treatment codes. The block size 6 will be used in the randomization schedule.

Neither the subjects nor the investigators will be aware of the treatment assignment for the subjects. The study drugs will be identical in number and appearance. Blinding will be maintained throughout the study by use of active or placebo dosage forms of similar appearance.

A subject's treatment assignment will not be broken until the end of the study unless medical treatment of the subject depends on knowing the study treatment the subject received. In the event that the blind needs to be broken because of a medical emergency, the investigator may unblind an individual subject's treatment allocation. As soon as possible, the investigator should first contact the medical monitor to discuss the medical emergency and the reason for revealing the actual treatment received by that subject. No investigator is in full rights to unblind a subject on medical reasons without prior consultation with the sponsor or medical monitor.

Eligible subjects will be stratified at randomization based on the presence or absence of a diagnosis of diabetes mellitus (diabetes mellitus: YES or NO).

4.3. Analysis Set

Intent-to-Treat (ITT) Set: All randomized subjects who signed the consent form and received at least one dose of study drug.

Modified Intent-to-Treat (mITT) Set: All randomized subjects who have a positive culture for Candida species at baseline and taking at least one dose of study drug.

Per-Protocol (PP) Set: All mITT subjects who meet all of the following criteria:

- Completed the study drug treatment;
- Have a TOC evaluation that includes documentation of signs, symptoms and collection of a vaginal culture;
- No major protocol deviation.

Safety Set (SS): All randomized subjects who received at least one dose of study drug and who have at least one post-baseline evaluation.

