first dose at the study center would complicate the administration of the second dose 12 hours later (e.g. first dose at 3 p.m. will require second dose at 3 a.m.), the subject can self-administer both doses at home to allow for a more convenient dosing schedule (e.g., 8 p.m. and 8 a.m.). Subjects will record study drug dosing details in their study diary.

Assessment of Clinical Cure (TOC [Day 11 ±3])

At the TOC visit (Day 8-Day 14), subjects will return any remaining medication as well as empty bottles of the study drug and treatment compliance will be evaluated. Subject diaries will be returned and reviewed. The investigators and the subjects will rate the signs and symptoms of infection, respectively, on the VSS Scale. A vaginal sample for fungal culture and for species identification and antifungal susceptibility testing will be obtained and sent to a designated central laboratory. An abbreviated physical exam, vital signs measurements and safety laboratory tests will also be performed.

If the baseline vulvovaginal symptoms have not noticeably improved or have worsened and the investigator considers that rescue antifungal medication may be needed, a vaginal sample should also be obtained for KOH testing by the local laboratory.

Follow up (Day 25 [±4])

At the FU visit, subjects will rate their symptoms of infection on the VSS Scale. Vulvovaginal samples for KOH testing and fungal culture should be obtained if there is persistence or recurrence of vulvovaginal symptoms. Only if symptoms are present, the investigator will perform a vulvovaginal examination to rate the subject's signs of infection.

All Visits

AEs and prior/concomitant medications will be assessed and documented at all visits.

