18.2 Analysis Populations

The study populations to be used in the analyses are defined as follows:

Intent-to-Treat (ITT) Population: All randomized subjects.

Modified Intent-to-Treat (mITT) Population: All randomized subjects who have a positive culture for *Candida* species at Baseline.

Per-Protocol (PP) Population: All mITT subjects who have completed the study drug treatment AND who have a TOC evaluation.

Safety Population: All randomized subjects who received at least one dose of study drug and who have at least one post-Baseline evaluation.

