18.4 Handling of Missing Data, Dose Adjustments, and Early Withdrawals

For the efficacy analyses, subjects who do not have a TOC (Day 8-Day 14) assessment will be assigned as treatment failures. For subjects who withdraw from the study early, every effort will be made to collect TOC visit information at the point of withdrawal.

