18.6.2 Efficacy Analyses

The efficacy analyses will be conducted using the mITT (primary analysis population), ITT and PP populations to evaluate ibrexafungerp vs. placebo.

The primary endpoint, percentage of subjects with clinical cure at TOC, will be analyzed using a Cochran Mantel Haenszel (CMH) test adjusted for site; the p-value and 95% confidence intervals will be presented. Missing Day 8-Day 14 (TOC) data for the primary endpoint will be imputed as failures in the analysis. A sensitivity analysis will be performed where subjects with missing values will be removed from the analysis. All other data will be analyzed as is with no imputation.

For other continuous efficacy endpoints, a two-way analysis of variance (ANOVA) model will be used including effects for treatment and site; p-values and 95% confidence intervals will be presented. For other categorical endpoints, the CMH test adjusted for site will be performed, and p-values and 95% confidence intervals will be presented.

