4.4. Handing of missing data

For categorical response endpoints including clinical outcome, mycological outcome, symptom outcome, and clinical improvement, subjects will be considered a non-responder for the non-responder imputation (NRI) analysis if they do not meet the clinical response criteria for categorical responses or are missing categorical response data at the specific visit. Randomized subjects without at least 1 post-baseline observation will also be defined as non-responder for the NRI analysis such that subjects who have a missing value at the TOC visit or FU visit will be assigned as treatment failures, i.e., non-responders or positive mycological outcome for the corresponding visit. Randomized subjects without study treatment will be excluded from all analysis.

5. Subject Disposition

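### The SAP adds a dosing condition to ITT and to the primary mITT set without declaring it, so no planned efficacy analysis keeps all randomised women

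*SAP*

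**What the plan says.** **Protocol.** Section 18.2 gives "Intent-to-Treat (ITT) Population: All randomized subjects" and nothing further. Its mITT definition begins "Modified Intent-to-Treat (mITT) Population: All randomized subjects who have a positive culture for" Candida species at baseline. Neither definition mentions dosing, and the synopsis agrees. Section 18.6.2 fixes the roles of the sets: "The efficacy analyses will be conducted using the mITT (primary analysis population), ITT and PP populations". Section 18.4 states that "subjects who do not have a TOC (Day 8-Day 14) assessment will be assigned as treatment failures", and Section 18.6.2 repeats this for the primary endpoint.

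**SAP.** Section 4.3 defines ITT as "All randomized subjects who signed the consent form and received at least one dose of study drug" and limits mITT to randomised women with a "positive culture for Candida species at baseline and taking at least one dose of study drug". Section 4.4 first makes randomised women with no post-baseline observation non-responders. It then ends: "Randomized subjects without study treatment will be excluded from all analysis". Sections 8 and 8.1.1 make this mITT set primary, with ITT and PP supportive. Section 11 lists two changes from the protocol, ANCOVA in place of ANOVA and the added diabetes factor. It does not mention the analysis sets.

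**Dosing.** The first dose is normally taken at the site. Where that would make the timing of the second dose awkward, Protocol 10.1.1 allows that "the subject can self-administer both doses at home". A randomised woman can therefore leave the site undosed. SAP 7.2.1 and 7.2.2 provide for zero tablets taken and a 0% compliance class.

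**The concern.** The two documents define the primary analysis set differently, and the SAP does not say that it has departed from the protocol. A change of primary population deserves declaration at least as much as a change of model for a secondary endpoint.

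Three things follow:

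- The set that the SAP calls ITT is not ITT. Because PP is a subset of mITT, no planned efficacy analysis includes every randomised woman.
- An undosed, culture-positive woman with no TOC assessment is a failure in the protocol's primary analysis and absent from the SAP's. Membership of the primary set then depends on something that happens after randomisation.
- SAP 5.1 presents disposition and reasons for discontinuation by the redefined sets, so undosed women can drop out of that account too. Protocol 18.3 asks for the number randomised and the reasons for discontinuation by group.

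There is also a gap. For a woman who was to take both doses at home, the main evidence of dosing is the diary and the tablet count, both collected at TOC (Protocol 12.5, 14.16, 14.17). If she never returns, SAP 7.2.1 leaves her cumulative dose missing. SAP 4.4 could then be read to make her a non-responder, because she has no post-baseline observation, or to exclude her as untreated.

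**Working it through.** **Inputs.** Protocol 18.1 gives cure rates of 50% and 30%, 2:1 allocation, 366 randomised (244 and 122), 20% culture-negative, 90% power and 5% type I error. Section 18.0 makes tests two-sided. The undosed share *u* is not in the documents. I assume 0% to 5%, with no TOC data for undosed women.

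**1. The plan's sample size.** With a pooled variance under the null and no continuity correction, the pooled rate is (0.30 + 2 × 0.50)/3 = 0.4333. The placebo arm needs

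n = [1.960 × √(1.5 × 0.4333 × 0.5667) + 1.2816 × √(0.30 × 0.70 + 0.50 × 0.50/2)]² / 0.20² = 93.2, rounded up to 94.

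The total is 94 + 188 = 282, with power 90.2%. The stated figure reproduces, and the point made here does not affect it.

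**2. Expected mITT.** 244 × 0.80 = 195.2 and 122 × 0.80 = 97.6, so about 195 + 98 = 293.

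**3. Equal undosed share in both arms.** Under the protocol rule undosed women stay in as failures. The rates become 0.50(1−u) and 0.30(1−u), and the difference is 20(1−u) points on 293 women. Under the SAP rule they are removed, so the difference stays at 20 points on 293(1−u) women.

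| u | Undosed of 366 | Of these in mITT | Difference, protocol rule | Difference, SAP rule | Power, protocol | Power, SAP |
|---|---|---|---|---|---|---|
| 0% | 0 | 0 | 20.0 | 20.0 | 91.4% | 91.4% |
| 1% | 4 | 3 | 19.8 | 20.0 | 90.9% | 91.1% |
| 2% | 7 | 6 | 19.6 | 20.0 | 90.4% | 90.8% |
| 3% | 11 | 9 | 19.4 | 20.0 | 89.9% | 90.5% |
| 5% | 18 | 15 | 19.0 | 20.0 | 88.8% | 89.9% |

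The SAP reports an odds ratio. At u = 5% it is (0.475/0.525)/(0.285/0.715) = 2.27 under the protocol rule and (0.50/0.50)/(0.30/0.70) = 2.33 under the SAP rule.

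**4. Unequal loss.**

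- Six undosed women, all on active: 0.50 × 189/195 = 48.5%, so the protocol rule gives 48.5 − 30.0 = 18.5 points against 20.0 under the SAP.
- Five undosed women, all on placebo: 0.30 × 93/98 = 28.5%, so the protocol rule gives 50.0 − 28.5 = 21.5 points against 20.0 under the SAP.

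The sign depends on which arm loses the women.

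**The case against.** The practical effect may be very small. The study is double-blind with matching tablets, so never starting treatment should not depend on the assigned arm. Dosing at the site is the default (Protocol 10.1.1, 14.14), and the accountability logs record administration to each subject (Protocol 12.4). A woman dosed at the site therefore has a record of at least one dose even if she never returns. This stands, and it limits the size of the problem.

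A reader might infer something stronger: that home-dosed women who are lost to follow-up are dropped as a rule, which would undo the missing-equals-failure rule and overstate the effect by 1 to 2 points. That range comes from treating half or all of the planned 10% withdrawals as having no dosing record. With all kept as failures the rates are 45% and 27% (18.0 points). With half dropped they are 47.4% and 28.4% (18.9), and with all dropped 50% and 30% (20.0). The documents do not support this reading, for four reasons:

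- SAP 4.4 excludes women without treatment. It does not tell the analyst to treat unknown dosing as no dosing, and SAP 7.2.1 keeps zero and missing apart.
- Taking both doses at home is the exception, so having half or all withdrawals undocumented is an upper-end assumption.
- Dosed women who withdraw without TOC data stay in the SAP's mITT set as failures.
- Unequal loss does not always favour the drug, as the placebo example shows.

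It would also be too strong to say that the protocol fails every undosed woman. One who attends TOC is scored as observed. The primary set loses only culture-positive undosed women; culture-negative ones are lost from ITT alone.

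A smaller remedy would be to declare and justify the change in SAP Section 11. That would cure the silence but still leave no all-randomised efficacy analysis.

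**Conclusion.** The point holds as an undeclared contradiction between protocol and SAP over the primary and ITT sets, together with an unstated rule for women whose dosing is unknown. This can be read from the text and needs no assumption.

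The numerical effect does rest on assumptions. With 0% to 5% undosed, equally in both arms and without TOC data, the SAP rule raises the expected difference by 0 to 1.0 point and power by 0 to 1.1 points. With five or six undosed women all in one arm, the two rules differ by about 1.5 points, in either direction. A predictable bias in favour of the drug under unequal loss is not shown. The case for changing the plan is that it should follow its own protocol and contain one true all-randomised analysis.

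**What to change.** Before unblinding:

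1. In SAP 4.3, restore the protocol definitions: ITT is all randomised women, and mITT is all randomised women with a positive baseline Candida culture.
2. Delete the last sentence of SAP 4.4. The Safety Set is unaffected, because its own definition already requires a dose.
3. State that undosed and dose-unknown women stay in their randomised arm, scored as observed if they have a TOC assessment and as non-responders if they do not.
4. Keep a dosed-only mITT as a sensitivity analysis.
5. Report undosed and dose-unknown women by arm in the disposition table.

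One consequential edit is needed. The SAP anchors baseline and time to resolution to the first dose, so it should name a fallback anchor, such as randomisation, for women with no known first dose.

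The cost is SAP wording only, with no new data, visits or sample size. The downside is that cure rates may be slightly less favourable.
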